h Serum samples are collected pre-infusion at each time point. Additional samples may be taken if clinically indicated in the event of IARs.

i For patients participating in Cohort 3 and switching to alglucosidase alfa at Week 27, pharmacokinetic sampling will be performed prior to infusion; at the end of infusion; and 2, 4, 6, and 8 hours after the end of infusion at Week 27 and prior to infusion and 2 hours after the end of infusion at Week 37; additionally in the 40 mg/kg dose cohort 12 to 16 hours after the end of infusion at Week 27.

j In the event patient requires ventilator support (invasive or non-invasive) at any time during study treatment the patient will be asked to complete a daily ventilator use diary. On a biweekly basis, the periods of ventilator use/day (daytime, nighttime, both) will be reported by the Investigator based on the ventilator use diary.

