- o Biochemistry assessments only for participants treated with alglucosidase alfa. Sampling is not required for Stage 2 - Cohort 3 participants randomized to treatment with alglucosidase alfa.
- p Serum samples are collected pre-infusion at each time point. Additional samples may be taken if clinically indicated in the event of IARs. Stage 2 Cohort 3 patients receiving alglucosidase alfa treatment do not require sampling of anti- alglucosidase alfa antibodies and neutralizing antibodies in anti-alglucosidase alfa antibody positive patients at Day 8, Week 5, Week 9, Week 13, Week 17, Week 21.
- q Pharmacokinetic sampling schedule: prior to infusion; at the end of infusion; and 2, 4, 6, and 8 hours after the end of infusion at Day 1 and Week 25 and prior to infusion and 2 hours after the end of infusion at Week 13; additionally in the 40 mg/kg dose cohort 12 to 16 hours after the end of infusion at Day 1 and Week 25. For Stage 2 - Cohort 3 participants randomized to treatment with alglucosidase alfa, sampling of

avalglucosidase alfa pharmacokinetics is not required at Day 1, Week 13 and Week 25. Pharmacokinetic blood samples are to be collected within 15 minutes of scheduled time: predose and all samples immediately following the end of the infusion through 8 hours post infusion.

r [REDACTED]

s Blood samples will be obtained as blood volume permits and will not exceed the blood volume collection limit of < 7 mL/kg over an 8-week period. Sampling is prioritized for safety labs (hematology, biochemistry, ADA) and PK [REDACTED]
[REDACTED]

t Time points are suggested time points.

u In the event patient requires ventilator support (invasive or non-invasive) at any time during study treatment the patient will be asked to complete a daily ventilator use diary. On a biweekly basis, the periods of ventilator use/day (daytime, nighttime, both) will be reported by the Investigator based on the ventilator use diary.

v Patients included in Cohort 3 on the basis of sub-optimal clinical response documented by motor scale and/or clinical development evaluation tools other than GMFM-88 or Pompe-PEDI will undergo assessment with those tools in combination with the prescribed/planned testing at screening/baseline and Week 25.

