10.1.2.2 One week following first infusion (Week 2 [Day 8])

The following will be performed one week following the date of the first infusion:

- Lab
 - Safety:
 - Biochemistry in patients receiving avalglucosidase alfa;
 - ADAs (with neutralizing antibodies in ADA positive patients) for anti-avalglucosidase alfa and anti-alglucosidase alfa antibodies for patients receiving avalglucosidase alfa;
 - ADAs (with neutralizing antibodies in ADA positive patients) for anti-alglucosidase alfa antibodies for patients receiving alglucosidase alfa;
 - Biomarkers:
 - Urine Hex4 sample collection;
 - Blood samples will be obtained as blood volume permits and will not exceed the blood volume collection limit of < 7 mL/kg over an 8-week period. Sampling is prioritized for safety labs (hematology, biochemistry, ADA) and PK and [REDACTED]
- AE collection;
- Concomitant medications/therapies.

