10.1.2.5 Monthly

The following assessments will be performed on a monthly basis (W5, W9, W13, W17, W21, and W25):

- Lab:
 - Biomarkers:
 - Urine Hex4 sample collection;
 - Urine β -HCG pregnancy test (females of childbearing potential only);
 - Safety:
 - Biochemistry in patients receiving alglucosidase alfa;

- ADAs (with neutralizing antibodies in ADA-positive patients) for anti-avalglucosidase alfa antibodies for patients receiving avalglucosidase alfa;
- Ventilator use diary;
- Eyelid position measurements;
- Vital signs (before, during, and following infusion: see [Section 1.2](#));
- IRT contact for IMP resupply;
- Infusion of IMP;
- ECG (at Week 5);
- Body weight;
- Physical examination (at Week 5, Week 9, and Week 13);
- AE collection;
- Prior/concomitant medications/therapies.

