10.1.2.6 Every 3 months

The following assessments will be performed at quarterly visits (W13 and W25):

- Physical examination;
- Body weight;
- Height/body length/head circumference;
- Lab:
 - Urine β -HCG pregnancy test (females of childbearing potential only);
 - Safety:
 - Hematology, biochemistry, and urinalysis;
 - ADAs (with neutralizing antibodies in ADA-positive patients) for anti-avalglucosidase alfa and anti-alglucosidase alfa antibodies for patients receiving avalglucosidase alfa, and anti-alglucosidase alfa antibodies only for patients in Stage 2-Cohort 3, who are randomized to receive alglucosidase alfa treatment at current stable dose (W13 only);
 - ADAs (with neutralizing antibodies in ADA positive patients) for anti-avalglucosidase alfa and anti-alglucosidase alfa antibodies (W25 only);
 - Biomarkers:
 - [REDACTED]
 - [REDACTED]
 - [REDACTED]
 - Urine Hex4 sample collection;

- Avalglucosidase alfa plasma PK sample collection (before and following infusion) in patients receiving avalglucosidase alfa;
 - For Cohort 1 and 2 patients and for Cohort 3 patients who are randomized in the avalglucosidase alfa group, this visit requires a stay at the site prior to and for at least 8 hours following the end of IMP infusion (Week 25 only).
 - For Cohort 2 patients and for Cohort 3 patients who are randomized in the avalglucosidase alfa group, another sample will be taken 12 to 16 hours after the end of IMP infusion (Week 25 only). If the Cohort 3 dose of avalglucosidase alfa is 20 mg/kg qow, this additional sample will not be taken.
- Blood samples will be obtained as blood volume permits and will not exceed the blood volume collection limit of < 7 mL/kg over an 8-week period. Sampling is prioritized for safety labs (hematology, biochemistry, ADA) and PK and [REDACTED]
[REDACTED]
[REDACTED]
[REDACTED]
- ECG;
- Vital signs (before, during, and following infusion: see [Section 1.2](#));
- Muscle biopsy (optional) at Week 25 only;
- Ventilator use diary;
- PFT (in patients who can reliably undergo testing and/or who are not invasively ventilated);
- 6MWT (in patients who are able to ambulate at least 40 meters [approximately 130 feet] without stopping and without an assistive device);
- GMFM-88/GMFCS-E&R
- Motor Skills Checklist;
- QMFT;
- Pompe-PEDI, Functional Skills Scale: Mobility Domain;
- Bayley-III/Leiter-3 scales;
- Echocardiography;
- Hearing testing;
- Eyelid position measurements;

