17.4.2 Amended protocol 02: 24 Mar 2020

Overall Rationale for the Amendment

Global changes

- In order to allow study participants to continue to receive the investigational medicinal product (IMP) after Week 145, the study has been extended to an additional period of up to 226 weeks (Week 371) or until alglucosidase alfa is approved in the patient's country, whichever comes first (refer to Appendix C [[Section 17.3.1](#)] for definition applicable for UK patients).
- In countries where it is permitted, home infusion of alglucosidase alfa in the extension period may be allowed (refer to Appendix C [[Section 17.3.3](#)] for France]).
- Clarifications were given regarding the conditions for temporary IMP discontinuation with DMC consultation.
- Clarifications were given regarding AESI related to LFT values that can fluctuate as part of the underlying Pompe disease.
- Clarification was given in the tertiary endpoints that the Motor Skills Checklist is completed in concert with the Gross Motor Function Classification System, Expanded and Revised.
- Clarification was given in the description of some tertiary endpoints.
- Clarification was given regarding the possibility of additional interim analysis for regulatory purpose during the extension period.
- Clarification was given regarding the order of motor assessments.
- As patients are no longer treated with alglucosidase alfa after Week 25 when entering the extension period, the collection of samples for analysis of anti-alglucosidase alfa antibodies was removed from the follow-up after primary analysis period (PAP).
- Sections 12, 13, and 14 were updated to reflect practices as outlined in the current protocol template.

France-specific requirement

- The option for home infusion added in this amended protocol 02 does not apply in France to be consistent with the French Health Authority position disallowing home infusion for all enzyme replacement therapies (ERT).

United Kingdom-specific requirement

- To comply with the United Kingdom (UK) position regarding the protocol language with regards to the study follow-up period duration.

Protocol amendment summary of changes table

Section # and Name	Description and Change	Brief Rationale

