2.4.4 Analyses of safety data

In general, for PAP, the summary of safety results will be presented by study cohort and treatment arm. For the overall avalglucosidase alfa treatment period, the summary of safety results will be presented by initial planned dose levels among avalglucosidase alfa patients. For Cohort 3 alglucosidase alfa patients, the summary of safety results for ETP will be presented in separate tables.

In the PAP analysis, the safety analyses will be carried out with patients by the actual treatment received, irrespective of the treatment the patient has been randomized to. The actual treatment received is defined as:

- avalglucosidase alfa if the patient receives at least one infusion with this drug in PAP;
- alglucosidase alfa if the patient only receives alglucosidase alfa in PAP.

In the ETP analysis and/or overall evaluation of avalglucosidase alfa safety, the safety analyses will be carried out by the following 3 groups:

- AVAL/AVAL in ETP includes data in ETP among patients who received avalglucosidase alfa in PAP and ETP;
- ALGLU/AVAL in ETP includes data in ETP among patients who received alglucosidase alfa in PAP and received avalglucosidase alfa in ETP;
- AVAL/AVAL and ALGLU/AVAL in overall avalglucosidase alfa treatment period includes data in PAP and/or ETP among patients who received avalglucosidase alfa in that period.

General rules

All safety analyses will be performed on the safety population as defined in [Section 2.3.1](#), unless otherwise specified, using the following common rules:

- The safety baseline value is defined the same as the baseline definition in [Section 2.1.1](#).
- The potentially clinically significant abnormality (PCSA) values are defined as abnormal values considered medically important by the Sponsor according to predefined criteria/thresholds based on literature review and defined by the Sponsor for clinical laboratory tests, vital signs, and ECG (PCSA version dated January 2014 [[Appendix B](#)]).
 - PCSA criteria will determine which patients had at least 1 PCSA during the treatment epoch (for PAP and ETP respectively), taking into account all evaluations performed during this period, including nonscheduled or repeated evaluations.
 - The number of all such patients will be the numerator for the on-treatment PCSA percentage; the denominator will be the number of patients assessed for that given parameter in the treatment epoch by treatment group on the safety population.

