2.4.4.3 Analyses of laboratory variables

Observed measurements and changes from baseline to study time points in biochemistry, hematology, and urinalysis will be descriptively summarized for each visit or study assessment (baseline and each post-baseline time point), by study cohort and treatment arm, as well as by dose levels among avalglucosidase alfa treated patients for the overall avalglucosidase alfa treatment period. This section will be organized by biological functions.

All laboratory values will be classified as normal, above normal, or below normal based on normal ranges provided by the laboratory. The n and % of patients with the following selected laboratory abnormalities of all laboratory variables, when applicable, will be summarized for each visit or study assessment.

- Blood chemistry:
 - Plasma/serum electrolytes: sodium, potassium,
 - Liver function: AST, ALT, alkaline phosphatase, gamma-glutamyl transferase, total bilirubin, indirect bilirubin, direct bilirubin,
 - Renal function: creatinine,
 - Metabolic panel: glucose, albumin, protein, cholesterol, triglycerides,
 - Potential muscle toxicity: CK, CK with MB fraction,
 - Brain natriuretic peptide (BNP).
- Hematology: hemoglobin, white blood cell count with differential count (neutrophils, eosinophils, basophils, monocytes, and lymphocytes), platelets.

Comparisons of the worst laboratory abnormalities with the baseline will be presented for each laboratory parameter listed above, when applicable. This analysis will be conducted for PAP and for the overall avalglucosidase alfa treatment period.

Individual listings of patients with potentially clinically significant abnormalities will be presented.

The incidence of PCSAs (list provided in [Appendix B](#)) at any time during the treatment-emergent adverse event period will be summarized by biological functions and treatment groups. The PCSA analyses will be conducted for PAP primarily. Similar analyses will be conducted for the overall avalglucosidase alfa treatment period.

Drug-induced liver injury

The liver function tests, namely AST, ALT, alkaline phosphatase, and total bilirubin, are used to assess possible drug-induced liver toxicity. The following analyses will be performed:

- Time to onset of the initial ALT or AST elevation ($>3 \times \text{ULN}$) and total bilirubin elevation ($>2 \times \text{ULN}$), whichever comes first will be analyzed using Kaplan-Meier estimates by study cohort and treatment arm, if necessary.

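### Unequal biochemistry sampling in the primary period (7 scheduled samples against 2) tilts the any-time abnormality displays against avalglucosidase alfa in Cohort 3

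*Protocol*

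**What the plan says.** The flow chart in Protocol 1.2.1 marks post-baseline biochemistry at Day 8 and Weeks 5, 9, 13, 17, 21 and 25. All of these except Weeks 13 and 25 carry footnote o, which ends: "Sampling is not required for Stage 2 - Cohort 3 participants randomized to treatment with alglucosidase alfa". Protocol 10.1.2.2 agrees for Day 8, listing "Biochemistry in patients receiving avalglucosidase alfa". Protocol 10.1.2.6 ("The following assessments will be performed at quarterly visits (W13 and W25") lists biochemistry with no restriction by arm.

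Two places read differently. The first sentence of footnote o names the other drug, and so does the monthly list in Protocol 10.1.2.5 ("The following assessments will be performed on a monthly basis (W5, W9, W13, W17, W21, and W25"), which has "Biochemistry in patients receiving alglucosidase alfa".

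On the analysis side, SAP 2.4.4 decides whether a patient had a PCSA by "taking into account all evaluations performed during this period, including nonscheduled or repeated evaluations", and divides by the number of patients assessed for that parameter. SAP 2.4.4.3 says PCSA incidence "will be summarized by biological functions and treatment groups", primarily for the PAP. It also compares each patient's worst laboratory abnormality with baseline. Nothing limits the between-arm display to common visits or reports how many samples each patient contributed.

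**The concern.** A count of patients with at least one abnormal value rises with the number of times each patient is tested. If one arm is tested seven times and the other twice, equal underlying fluctuation gives unequal percentages. The protocol expects such fluctuation in liver tests: its Amendment 02 rationale (17.4.2) refers to "AESI related to LFT values that can fluctuate as part of the underlying Pompe disease".

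Cohort 3 controls are the only concurrent randomised reference for how often these abnormalities arise without the new drug. If their rate is low partly because they were tested less, part of the disease's natural variation will look like an effect of avalglucosidase alfa. Laboratory AESIs (ALT, AST, bilirubin and creatinine rises, SAP 2.1.3.1) are detected from the same samples and share the problem.

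**Working it through.** The plan states no figure to reproduce, so the check is a count followed by a null calculation.

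**Samples per arm (scheduled, post-baseline, PAP)**
- Avalglucosidase alfa: Day 8, Weeks 5, 9, 13, 17, 21, 25 = 7.
- Cohort 3 control: 7 less the 5 footnote-o visits (Day 8, Weeks 5, 9, 17, 21) = 2, at Weeks 13 and 25.

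**Independent samples.** Let p be the chance that one sample crosses a limit, equal in both arms. P(at least one in m) = 1 − (1 − p)^m. The documents give no p, so a range is shown.
- p = 0.01: 6.8% (m = 7) against 2.0% (m = 2)
- p = 0.05: 1 − 0.95^7 = 30.2% against 1 − 0.95^2 = 9.75%
- p = 0.10: 52.2% against 19.0%
- p = 0.20: 79.0% against 36.0%

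**Correlated samples.** Values within a patient are unlikely to be independent. A beta-binomial with within-patient correlation ρ has a = p(1 − ρ)/ρ and b = (1 − p)(1 − ρ)/ρ, and P(at least one in m) = 1 − ∏ (b + j)/(a + b + j) for j = 0 to m − 1. For p = 0.05 and ρ = 0.5, a = 0.05 and b = 0.95. With m = 2 the product is 0.95 × 0.975 = 0.926, giving 7.4%. With m = 7 it is 0.877, giving 12.3%. The documents give no ρ either.

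Results at p = 0.05, with 5 patients per arm (Cohort 3 is at least 10, randomised 1:1):

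| ρ | 7 samples | 2 samples | Ratio | Expected affected of 5 | P(avalglucosidase alfa shows more) | P(control shows more) |
|---|---|---|---|---|---|---|
| 0 | 30.2% | 9.75% | 3.1 | 1.51 vs 0.49 | 0.665 | 0.097 |
| 0.3 | 16.9% | 8.3% | 2.0 | 0.84 vs 0.42 | 0.452 | 0.164 |
| 0.5 | 12.3% | 7.4% | 1.7 | 0.62 vs 0.37 | 0.361 | 0.182 |
| 0.7 | 8.9% | 6.4% | 1.4 | 0.45 vs 0.32 | 0.285 | 0.188 |
| 0.9 | 6.2% | 5.5% | 1.1 | 0.31 vs 0.27 | 0.214 | 0.185 |

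The gap shrinks as correlation rises but never changes sign. It closes only at perfect correlation, or at p of 0 or 1.

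**If Protocol 10.1.2.5 were literal.** Avalglucosidase alfa would have 3 samples (Day 8, Weeks 13 and 25) and control 6 (Weeks 5, 9, 13, 17, 21, 25). At p = 0.05 and independence that is 14.3% against 26.5%, so the bias would reverse. Weeks 13 and 25 would still be the common visits.

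**Restricted to Weeks 13 and 25.** Both arms have m = 2, so the null expectation is the same: 9.75% each at p = 0.05 with independence, 7.4% each at ρ = 0.5.

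**The case against.** The strongest reply is that a fair comparison already exists. SAP 2.4.4.3 tabulates the number and percentage of patients with selected laboratory abnormalities at each visit. SAP 2.5.4 and 2.5.5 use nominal visits and leave unscheduled values out. At Weeks 13 and 25 these tables put both arms on equal sampling. This stands, so a reader who infers that the plan offers no like-for-like laboratory comparison would be wrong. But those tables use normal-range limits and do not replace the any-time PCSA and worst-value displays.

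Second, a reader might infer a two- to threefold distortion. That holds only for independent or weakly correlated samples. The AESI rules in Protocol 10.4.1.3 provide for patients whose baseline ALT or AST is already at or above the ULN, and for such patients independence is implausible. At ρ = 0.5 the ratio is 1.7, and at 0.9 it is 1.1.

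Third, the rationale in Protocol 17.4.2 speaks of liver tests only. It does not support saying that creatinine, electrolytes or glucose fluctuate with the disease.

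Fourth, the primary objective is the safety profile of avalglucosidase alfa; comparison with alglucosidase alfa is stated only for preliminary efficacy. SAP 2.4.4 plans no inferential safety tests. Denser sampling of the new drug suits that objective, and individual listings are planned. All this stands, so there is no type I error problem and no reason here to change the sampling. It does not make unequal any-time percentages comparable when they are printed by arm.

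Fifth, SAP 2.4.4.3 names treatment groups for PCSAs but not for the worst-value comparison. That grouping comes from the general PAP rule in SAP 2.4.4.

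**Conclusion.** The point holds in a limited form. On the reading fixed by the last sentence of footnote o and, for Day 8, by Protocol 10.1.2.2, scheduled sampling is 7 against 2. The any-time biochemistry PCSA and worst-value displays, and detection of laboratory AESIs, then lean against avalglucosidase alfa when there is no drug effect. The direction is firm on that reading. The size is not: at p = 0.05 the difference runs from about 20 percentage points (independent samples) through 5 (ρ = 0.5) to under 1 (ρ = 0.9), and both p and ρ are assumptions. Unscheduled samples also count and could move actual numbers in either arm.

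The effect is confined to biochemistry. Scheduled haematology, urinalysis and ECG are the same in both arms, so a reader should not extend it to laboratory or safety abnormalities in general.

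The conflicting drug names are probably a transcription matter. The Clinical Trial Summary, as read, also interchanges them, with controls on alglucosidase alfa offered a switch to alglucosidase alfa. The four exempt visits after Day 8 rest on footnote o alone, so its first sentence and Protocol 10.1.2.5 should be checked in the source and reconciled if they really differ.

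**What to change.** In SAP 2.4.4.3, for the Cohort 3 between-arm display in the PAP:

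- Add biochemistry PCSA counts and worst-value-versus-baseline counts restricted to the scheduled visits common to both arms (Weeks 13 and 25).
- Keep the all-evaluations table for describing avalglucosidase alfa safety, and show in it the number of samples per patient.
- Footnote that table and the laboratory-AESI table as not comparable between arms because sampling is unequal. A footnote is enough for AESIs: they are adverse event records with onset dates, and limiting them to two visits would mean re-deriving them from laboratory values.

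The cost is one extra table per display from data already collected, with no change to sampling. The small downside is that the common-visit table uses fewer samples and can miss events between visits, which is why the full table stays beside it. The fix works whichever way the drug-name question is settled, since Weeks 13 and 25 are common to both arms on either reading.

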1.2.3 Extension period (Week 37 to Week 145)

Period	Extension Period									
Timing	9 Month (Week 37)	12 Month (Week 49)	15 Month (Week 61)	18 Month (Week 73)	21 Month (Week 85)	24 Month (Week 97)	27 Month (Week 109)	30 Month (Week 121)	33 Month (Week 133)	36 Month (Week 145)
Visit^a	V22	V28	V34	V40	V46	V52	V58	V64	V70	V76
Visit at clinical site	X	X	X	X	X	X	X	X	X	X
Concomitant medications/therapies	X	X	X	X	X	X	X	X	X	X
Study treatment administration										
IRT contact (Dispensing)	X	X	X	X	X	X	X	X	X	X
avalglucosidase alfa infusion ^b	X	X	X	X	X	X	X	X	X	X
Vital signs ^c	X	X	X	X	X	X	X	X	X	X
Safety										
Urine pregnancy test ^{d,e}	X	X	X	X	X	X	X	X	X	X
Physical examination ^f	X	X	X ^g	X ^g		X		X		X
Height/body length/head circumference ^h	X	X	X	X		X		X		X
Body weight ^e	X	X	X	X	X	X	X	X	X	X
ECG ⁱ	X ^g	X		X		X		X		X
Hematology, urinalysis		X		X		X		X		X
Biochemistry ^j	X ^k	X ^k	X ^k	X ^k	X	X	X	X	X	X
Anti-avalglucosidase alfa antibodies (with testing for neutralizing antibodies in anti-avalglucosidase alfa antibody positive patients) ^l	X ^m	X ^m	X	X	X	X	X	X	X	X
Adverse event collection	X	X	X	X	X	X	X	X	X	X
Pharmacokineticsⁿ										
avalglucosidase alfa plasma samples	X	X								
Pharmacodynamics										
Urine Hex4 samples ^o		X		X		X		X		X
Muscle biopsy (optional) ^q		X ^g								X
Efficacy										
Ventilator use diary ^r	X	X	X	X	X	X	X	X	X	X
GMFM-88, GMFCS-E&R		X		X		X		X		X
Motor Skills Checklist		X		X		X		X		X
QMFT		X		X		X		X		X
Pompe-PEDI, Functional Skills Scale: Mobility Domain		X		X		X		X		X
Bayley-III / Leiter-3 scales ^s		X		X		X		X		X
Echocardiography ^t		X		X		X		X		X
Hearing testing ^t		X		X		X		X		X
Eyelid position measurements ^u		X		X		X		X		X
PedsQL Generic Core Scale		X		X		X		X		X

Period	Extension Period									
Timing	9 Month (Week 37)	12 Month (Week 49)	15 Month (Week 61)	18 Month (Week 73)	21 Month (Week 85)	24 Month (Week 97)	27 Month (Week 109)	30 Month (Week 121)	33 Month (Week 133)	36 Month (Week 145)
Visit ^a	V22	V28	V34	V40	V46	V52	V58	V64	V70	V76
questionnaire ^V										
Pediatric Pain Questionnaire ^W		X		X		X		X		X
Pain VAS ^W		X		X		X		X		X
PFT ^X		X		X		X		X		X
6MWT ^Y		X		X		X		X		X
Pharmacogenetics										

6MWT = 6-minute walk test; ADA = anti-drug antibodies; β-hCG = beta-human chorionic gonadotropin; BNP = brain natriuretic peptide; CK = creatine kinase; CRF = case report form; [REDACTED]; ECG = electrocardiogram; EDTA = Ethylenediaminetetraacetic acid; EOS = end of study; ERT = enzyme replacement therapy; GMFCS-E&R = Gross Motor Function Classification System – Expanded and Revised; GMFM-88 = Gross Motor Function Measure-88; IRT = interactive response technology; PedsQL = pediatric quality of life inventory; Pompe-PEDI = Pompe Pediatric Evaluation of Disability Inventory; PE = physical examination; PFT = pulmonary function testing; QMFT = Quick Motor Function Test; [REDACTED]; VAS = visual analog scale

- a In case of temporary treatment discontinuation, visit and assessment schedules will be adapted to the absence of infusion of alvalglucosidase alfa as outlined in [Section 10.1.7](#). Procedures and assessments are not presented in the chronological order in the flow chart. Refer to [Section 10.1](#) for the recommended order of procedures and assessments. Visits that are longer due to multiple assessments or procedures (eg, motor assessments, echocardiography, questionnaires) may be carried out over several days (refer to [Section 10.1](#)). Patients will be required to remain in the hospital or the infusion center for observation of AEs for 1 hour after each infusion. Patients may be required to stay for a longer observation period at the Investigator's discretion. In case the patient does not stay for this observation period (eg, as part of contingency measures for a regional or national emergency that is declared by a governmental agency), the Investigator (or appropriate designee) will contact the patient or their legally authorized representative (for pediatric patients) to ensure that no adverse event occurred during the observational period. For patients undergoing home infusion (as per conditions and instructions provided in [Section 8.9.2](#)) visit at clinical site is not required for infusion only visits. Refer to [Section 10.1.3](#) for the concerned weeks details. If alvalglucosidase alfa is approved in the patient's country before the patient reaches Week 145, the Week 145 visit will be performed as the end of treatment visit.
- b Alvalglucosidase alfa to be administered at study site every other week. As per conditions and instructions provided in [Section 8.1.2](#), alvalglucosidase alfa infusion may occur at home.
- c At every infusion. Vital signs include heart rate, systolic and diastolic blood pressure, respiratory rate, temperature, and oxygen saturation and are to be assessed prior to infusion, with each infusion rate change, at the end of the infusion and at the end of the post-infusion observation period. Collection windows are ±15 minutes.
- d Female patients of childbearing potential only will have a urine β-hCG test.
- e Monthly.
- f Physical examination CRF will ask physician to record current muscle pain and cramps specifically at each PE assessment. Tanner stage will be assessed as part of the PE assessment at Week 49, Week 97 and Week 145.
- g For Stage 2 - Cohort 3 for patients switching to alvalglucosidase alfa only.
- h To be measured at screening/baseline, every 3 months up to Week 73 and then every 6 months until Week 145/EOS in all patients.
- i 12-lead ECG after at least 15 minutes in supine position (if supine is feasible for the patient). Review should be done at the site in a timely manner to determine if there are any safety concerns and for clinical management of the patient. In addition, reading will be done by central reader for analyses purposes only.
- j Biochemistry panel will include BNP and CK.
- k Biochemistry in all patients will additionally be collected monthly for the first 6 months of the extension period (Week 29, Week 33, Week 37, Week 41, Week 45, and Week 49) and for patients who switch to alvalglucosidase alfa in Stage 2 – Cohort 3 for 6 more months (Week 53, Week 57, Week 61, Week 65, Week 69, Week 73).
- l Serum samples are collected pre-infusion at each time point. Additional samples may be taken if clinically indicated in the event of IARs.
- m Anti-alvalglucosidase alfa antibodies (with testing for neutralizing antibodies for alvalglucosidase alfa antibody positive patients) in Stage 2 - Cohort 3 alvalglucosidase alfa switch patients will be collected monthly for the first 6 months of the extension period (Week 29, Week 33, Week 37, Week 41, Week 45, Week 49).
- n For patients participating in Cohort 3 and switching to alvalglucosidase alfa at Week 27, pharmacokinetic sampling will be performed prior to infusion; at the end of infusion; and 2, 4, 6, and 8 hours after the end of infusion at Week 49 and prior to infusion and 2 hours after the end of infusion at Week 37; additionally in the 40 mg/kg dose cohort 12 to 16 hours after the end of infusion at Week 49.
- o [REDACTED]

- p* Blood samples will be obtained as blood volume permits and will not exceed the blood volume collection limit of < 7 mL/kg over an 8-week period. Sampling is prioritized for safety labs (hematology, biochemistry, ADA) and PK and [REDACTED]
[REDACTED].
- q* Time points are suggested time points.
- r* In the event patient requires ventilator support (invasive or non-invasive) at any time during study treatment the patient will be asked to complete a daily ventilator use diary. On a biweekly basis (including for patients receiving home infusions, see [Section 8.9.2](#)), the periods of ventilator use/day (daytime, nighttime, both) will be reported by the Investigator based on the ventilator use diary.
- s* The Bayley-III will be administered to patients from 1 month of age until the maximum score on each of the 3 administered scales has been obtained. Once the maximum score for a scale has been achieved, only the remaining scales will be administered. Bayley-III is to be discontinued when the patient reaches 42 months of age. Leiter-3 Scale assessment is to be performed at the last assessment of the Bayley-III Scales prior to the patient reaching 42 months of age. In case the developmental level of an individual patient is below the level required for the Leiter-3 Scale assessment, the patients should be assessed by the Bayley-III regardless of the patient's age.
- t* Hearing testing includes audiogram and brainstem auditory evoked potentials.
- u* Separate informed consent will be sought to permit for the acquisition and use of photographs of the patient's eyes in order to allow for independent review of eyelid position measurements by a central reader.
- v* PedsQL Generic Core Scales will be used in pediatric patients 2 years and older, using age appropriate reports
- w* Pain will be assessed by PedsQL Pediatric Pain Questionnaire for patients >5 years of age. Observer reported Pain VAS will be recorded in patients of all ages.
- x* Pulmonary function tests are not required for patients unable to reliably undergo testing or for patients who are invasively ventilated.
- y* 6MWT in patients who are able to ambulate at least 40 meters (approximately 130 feet) without stopping and without an assistive device.

